6. TREATMENT

6.1 DESCRIPTION OF TREATMENT

6.1.1 Drug Formulation and Supply

PM01183 drug product (DP) is presented as a lyophilized powder for concentrate for solution for infusion in 4-mg vials, which will be supplied by the Sponsor for the purposes of this study.

Before use,

For administration to patients as an i.v. infusion, reconstituted vials are diluted with glucose 50 mg/ml (5%) solution for infusion or sodium chloride 9 mg/ml (0.9%) solution for infusion.

For details on reconstitution/dilution, please refer to the IB and Preparation Guide for Infusion. PM01183 reconstitution/dilution records will be kept at the site.

The full composition of the PM01183 4-mg vials and the reconstituted solution per ml is as shown in [Table 5](#).

6.2 ADMINISTRATION OF THE STUDY MEDICATION

PM01183 will be administered over a _____ (either on 5% glucose or 0.9% sodium chloride), through a central catheter, or over _____ if administered through a peripheral line, always over one hour at a fixed infusion rate

6.3 STARTING DOSES AND SCHEDULE

Starting dose will be 3.2 mg/m². Dose will be capped at BSA of 2.0 m² (i.e., dose will not exceed 6.4 mg).

Patients will receive PM01183 i.v. as a one-hour infusion on Day 1 every three weeks (q3wk) (three weeks = one treatment cycle).

6.4 PROPHYLACTIC MEDICATION

All patients will receive standard antiemetic prophylaxis before each treatment infusion. The i.v. formulations of these agents must be used in this setting:

- Corticosteroids (dexamethasone 8 mg or equivalent).
- Serotonin (5-HT₃) antagonists (ondansetron 8 mg or equivalent).
- Extended treatment with oral 5-HT₃ antagonists and oral dexamethasone for two consecutive days.
- If necessary, and in addition to the above, administration of 10 mg of oral or i.v. metoclopramide (or equivalent) every eight hours.

Aprepitant and equivalent agents (e.g., fosaprepitant) are forbidden in patients treated with PM01183.

For the purpose of safety evaluations, an optimal prophylaxis is defined as all the aforementioned allowed medications at their respectively maximum dose.

6.5 CRITERIA FOR TREATMENT CONTINUATION

Further treatment cycles (i.e., Cycle 2 or subsequent) will be administered every q3wk (± 48 hours) if the patient fulfills all the re-treatment criteria defined in [Table 6](#).

Table 6. Criteria for treatment continuation.

Variable	Re-treatment (Day 1)
ECOG PS	≤ 2
Hemoglobin*	≥ 8.0 g/dl
ANC	≥ 1.5 × 10 ⁹ /l
Platelets	≥ 100 × 10 ⁹ /l
AST/ALT	≤ 3.0 × ULN
Total bilirubin or direct bilirubin	≤ 1.5 × ULN or × ULN
Albumin	≥ 3 g/dl
Serum creatinine	≤ 1.5 × ULN or creatinine clearance ≥ 30 ml/min
CPK	Grade ≤ 1
Other non-hematological drug-related AEs (except isolated increased GGT and/or AP; grade 2 asthenia, constipation, alopecia, peripheral neuropathy, or non-optimally treated nausea and/or vomiting)	Grade ≤ 1
Active infection (including sepsis) and/or bleeding (any grade)	Absence

* Patients may receive packed red blood cells (PRBC) transfusion and/or erythropoietin (EPO) treatment, if clinically indicated, to increase/maintain adequate hemoglobin levels.

AE(s), adverse event(s); ANC, absolute neutrophil count; AP, alkaline phosphatase; AST/ALT, aspartate aminotransferase/alanine aminotransferase; CPK, creatinine phosphokinase; ECOG, Eastern Cooperative Oncology Group; GGT, gamma-glutamyltransferase; PS, performance status; ULN, upper limit of

Variable	Re-treatment (Day 1)
----------	----------------------

normal.

If a patient does not meet the requirements for re-treatment on Day 1 of any following cycle, regardless of the reason, re-assessments will be performed at least every 48-72 hours. Treatment will be then withheld, up to a maximum of three weeks beyond its due date, until appropriate recovery.

Patients not meeting re-treatment criteria after a maximum 3-week delay must be withdrawn from trial. In case of objective clinical benefit, the patient could continue receiving the treatment (upon the Sponsors' agreement).

For any delay due to treatment-related adverse events lasting for more than one week, a dose reduction must be implemented upon recovery, following the rules explained in the next section (Section 6.6).

6.6 DOSE REDUCTION

Patients may continue the study treatment at a reduced dose if they present any of the following:

- Grade ≥ 3 treatment-related non-hematological toxicity. Exceptions are: grade ≥ 3 nausea and/or vomiting not optimally treated, grade 3 asthenia lasting ≤ 3 days, grade 3 diarrhea lasting ≤ 2 days or not optimally treated, grade 3 transient ALT/AST elevations which are rapidly reversible and not leading to subsequent delays, and non-clinically relevant biochemical abnormalities.
- Grade 4 thrombocytopenia or grade 3 thrombocytopenia concomitantly with grade ≥ 3 bleeding.
- Grade 4 neutropenia, any grade febrile neutropenia or neutropenia associated with infection/sepsis.
- Frequent or prolonged (>1 week) dose delays due to treatment-related adverse events.

Patients who experience grade 3/4 hypersensitivity reactions will be discontinued from study treatment.

Dose reduction levels are shown in [Table 7](#).

Table 7. Criteria for dose reduction.

Dose reduction	PM01183 dose (mg/m ²) *
1 (starting dose)	3.2 **
-1	2.6
-2	2.0

*Dose rounded to the first decimal.

**Dose will be capped at BSA of 2.0 m² (i.e., dose will not exceed 6.4 mg).

BSA, body surface area; ECOG, Eastern Cooperative Oncology Group; PS, performance status.

Up to two dose reductions are allowed per patient.

Patients who continue to experience treatment-related toxicity and/or frequent dose delays after permitted dose reductions must be withdrawn from the study. They can continue receiving the study medication if objective clinical benefit is adequately documented by the Investigator, and upon agreement with the Sponsor. Once the dose has been reduced for an individual patient, it will not be re-escalated under any circumstances.

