5.7 EVALUATIONS DURING TREATMENT

The following assessments will be done while the patient is on treatment ([Table 4](#)).

Table 4. Evaluations during treatment.

	ASSESSMENT	TIME
1. Clinical examination	
 Complete physical examination, including weight and calculation of BSA. Dose will be adjusted if BSA change is $\geq 10\%$ (higher or lower) of the previous value. 	Day 1 of each cycle (always prior to PM01183 infusion).*
	
 Performance status (ECOG PS). Vital signs: heart rate, blood pressure and body temperature. 	Day 1 of each cycle (always prior to PM01183 infusion).*
	
 Concomitant therapies. 	Throughout the “on treatment” period.**
2. Laboratory tests	
 Coagulation panel: PT/INR and PTT. 	Day 1 of each cycle (always prior to PM01183 infusion).*
	
 Hematology: Hemoglobin, platelet counts, and differential WBC counts (including neutrophils, monocytes and lymphocytes). Biochemistry A: Serum electrolytes (Na⁺, K⁺, Cl⁻), AST, ALT, AP, GGT, total bilirubin (direct bilirubin to be measured only if total bilirubin is $>1.5 \times \text{ULN}$), LDH, creatinine, glucose, and CPK. 	
Cycle 1 and 2: Day 1, 8 and 15 (always prior to PM01183 infusion).*
 
Two blood samples (24 hours and 72 hours after the end of PM01183 infusion) will be collected at the same time than PK samples #6 and #7 in Cycle 1 for monocyte count.
 
Further cycles: Day 1 of each cycle (always prior to PM01183 infusion).*
 
From Cycle 2 onwards, Hematology and Biochemistry A tests on Days 8 and 15 are to be performed only in patients who present biochemical grade ≥ 3 or hematological grade > 4 treatment-related toxicities, or who required dose adjustments due to hematological or biochemical abnormalities in the preceding cycle.
 
Any patient presenting a grade ≥ 3 treatment-related AE should have all relevant tests re-assessed at least every 48-72 hours until recovery to grade ≤ 2.
 
Any patient having febrile neutropenia of

	ASSESSMENT	TIME
		any grade, grade 4 neutropenia, and/or grade 4 thrombocytopenia, should have relevant tests repeated daily until recovery to grade ≤ 3 and up to the next day after fever resolution, if applicable.

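### The dose cap is worded as two limits that coincide only at 3.2 mg/m² and is marked on that row only, so the documents do not settle what cap applies after a dose reduction

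*Protocol*

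**What the plan says.** Protocol Section 6.3, which concerns starting doses, reads: "Starting dose will be 3.2 mg/m². Dose will be capped at BSA of 2.0 m² (i.e., dose will not exceed 6.4 mg". The synopsis entry on starting doses says the same.

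Table 7 in Section 6.6 lists three levels: 3.2 (starting dose), 2.6 (level -1) and 2.0 mg/m² (level -2). A double asterisk on the 3.2 entry leads to the footnote "Dose will be capped at BSA of 2.0 m² (i.e., dose will not exceed 6.4 mg". The 2.6 and 2.0 entries carry no such mark. Synopsis Table 3 is marked in the same way, so the placement is not a slip in a single table. A second footnote, on the dose column as a whole, adds "Dose rounded to the first decimal".

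On reductions, Section 6.6 states "Up to two dose reductions are allowed per patient" and rules out re-escalation. Section 6.5 makes a reduction compulsory after a treatment-related delay of more than one week: "a dose reduction must be implemented upon recovery". Section 5.7 has the dose recalculated when BSA changes by 10% or more and does not mention the cap. Neither the protocol nor the SAP prints a maximum in mg for level -1 or -2, or says which limit governs there.

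**The concern.** The cap joins a BSA limit and a mg limit as though they were one rule. They are one rule only at the starting level. Once a patient with BSA above 2.0 m² is reduced, a site can read the text in three ways:

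- **A:** the BSA limit of 2.0 m² applies at every level.
- **B:** 6.4 mg is a ceiling at every level.
- **C:** the cap belongs to the starting row only, as the footnote mark shows.

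These give different doses to identical patients. Under B and C the first step is smaller than the table implies, and at high enough BSA it disappears.

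Three features of the protocol make the dose in mg matter. Section 1.10.1.3 reports that clearance was unrelated to BSA, so exposure follows mg rather than mg/m². Section 6.6 triggers a reduction after events such as febrile neutropenia, grade 4 neutropenia or thrombocytopenia, or grade 3 or higher non-hematological toxicity, and Section 1.12 shows what a step of similar size (20%, from 4.0 to 3.2 mg/m²) is relied on to do: febrile neutropenia was 14% at the higher dose and 6% at the lower. Finally, only two reductions are available, and needing more ends treatment unless benefit is documented and the sponsor agrees. A large patient could use up one of the two for little change in dose.

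In the analysis, relative dose intensity and the dose-reduction counts (SAP Section 8.4 and Tables 12.1.3.2 to 12.1.3.4) would partly reflect which reading each site took.

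**Working it through.** **Inputs.** Levels of 3.2, 2.6 and 2.0 mg/m² (Table 7), and cap limits of BSA 2.0 m² and 6.4 mg (Section 6.3 and Table 7). The BSA values above 2.0 m² are an assumed range, because the documents give no distribution.

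**The protocol's own figure.** 3.2 × 2.0 = 6.4 mg, so the stated cap is reproduced exactly.

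**Where the two limits agree.** At BSA 2.0 m² the three levels give 6.4, 5.2 and 4.0 mg. The BSA at which each level reaches 6.4 mg is:

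- 6.4/3.2 = 2.00 m² at the starting level
- 6.4/2.6 = 2.46 m² at level -1
- 6.4/2.0 = 3.20 m² at level -2

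The limits therefore coincide at 3.2 mg/m² and nowhere else.

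**Level -1 under each reading.** Starting dose = min(3.2 × BSA, 6.4), which is 6.4 mg for every BSA of 2.0 m² or more. Level -1 is 2.6 × min(BSA, 2.0) under A, min(2.6 × BSA, 6.4) under B, and 2.6 × BSA under C. The change is measured from 6.4 mg.

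| BSA (m²) | A: BSA limit at every level | B: 6.4 mg ceiling | C: starting row only |
|---|---|---|---|
| 2.0 | 5.20 mg (-18.75%) | 5.20 mg (-18.75%) | 5.20 mg (-18.75%) |
| 2.1 | 5.20 mg (-18.75%) | 5.46 mg (-14.7%) | 5.46 mg (-14.7%) |
| 2.2 | 5.20 mg (-18.75%) | 5.72 mg (-10.6%) | 5.72 mg (-10.6%) |
| 2.3 | 5.20 mg (-18.75%) | 5.98 mg (-6.6%) | 5.98 mg (-6.6%) |
| 2.4 | 5.20 mg (-18.75%) | 6.24 mg (-2.5%) | 6.24 mg (-2.5%) |
| 2.5 | 5.20 mg (-18.75%) | 6.40 mg (0%) | 6.50 mg (+1.6%) |

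If the rounding footnote is taken to apply to the dose in mg, the first reduction is already zero from 6.35/2.6 = 2.44 m² under B. Under C it is zero from the same point until the rounded dose exceeds 6.4 mg.

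**Level -2.** Under A: 2.0 × 2.0 = 4.0 mg, a reduction of 37.5% from the start. Under B and C: 2.0 × 2.2 = 4.4 mg (-31.25%) at BSA 2.2 m², and 2.0 × 2.5 = 5.0 mg (-21.9%) at 2.5 m². Level -2 stays below the starting dose throughout the range examined. At BSA 2.5 m² two sites could still give 4.0 mg and 5.0 mg to identical patients.

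**The case against.** The readings are not equally natural. The operative clause is the BSA limit, and the 6.4 mg figure sits in a parenthesis that can be taken as working that clause out at the starting dose. Section 6.3 and the synopsis state the cap outside any table row. Read that way at every level, both steps survive in full. This part of the objection stands: a sensible site may well dose this way, and the text permits it. It does not settle the matter, because Section 6.3 is about starting doses and both tables mark the cap on the starting row alone.

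A reader might infer that the protocol directs sites to give a reduced dose equal to or above the starting dose. The documents do not support that. Sections 6.5 and 6.6 speak of a reduction and a reduced dose, and under reading C the 6.5 mg at BSA 2.5 m² also breaks the 6.4 mg limit. What the figures show is a conflict between the footnote placement and the surrounding text.

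The SAP would not hide the problem. Listing 12.1.3.1 prints the previous dose beside the reduced dose, Listing 14.1.20 shows intended and total dose, and cumulative dose is in mg. A trivial reduction would be visible per patient, although the summary counts would still record it as a reduction.

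**Conclusion.** The point holds as a gap and inconsistency in the dosing text. The cap is marked on one row, its two limits agree at one level, and nothing states what applies after a reduction.

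The size depends on the reading and on BSA. Under the BSA limit at every level there is no loss. Under the other two readings the first reduction falls from 18.75% to between 14.7% and 2.5% over BSA 2.1 to 2.4 m², and is absent or slightly reversed from about 2.46 m².

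It would be tempting to conclude that reductions fail in capped patients generally. That goes too far. Complete loss concerns only the first step, only at very high BSA, and only under two of the three readings. The documents give no BSA distribution, so neither the number of patients affected nor that any were affected can be shown.

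No sample size, power or alpha figure depends on this. It deserves correction because the reduction responds to toxicity, is compulsory in some circumstances, and the ambiguity is cheap to remove.

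**What to change.** The sponsor should reconcile Section 6.3, Table 7 in Section 6.6, and the synopsis entries on starting dose and dose reduction (synopsis Table 3). The protocol should then state one form of the cap and say whether it applies at each of the three dose levels. The result should be consistent with the requirement in Sections 6.5 and 6.6 that a reduction yields a reduced dose. Which form of the cap applies is for the sponsor to decide, and none is proposed here.

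The cost is a reworded footnote and matching sentences in an amendment or clarification to sites. It needs no additional patients, visits or procedures, and no change to the statistical design.

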5.2.1.2 Reasons for Treatment Discontinuation

Patients will receive the study treatment while it is considered to be in their best interest. Specifically, treatment will continue until:

- Disease progression.
- Unacceptable toxicity.
- Treatment delay > three weeks from the treatment due date (except in case of clear clinical benefit, upon Sponsors' approval).
- Requirement of > two dose reductions.
- Intercurrent illness of sufficient magnitude to preclude safe continuation of the study.
- A major protocol deviation that may affect the risk/benefit ratio for the participating patient.
- Investigator's decision.
- Non-compliance with study requirements.
- Patient's refusal.

Patients who are withdrawn for any reasons must not be re-treated in the context of this study at any time. For follow-up activities, please refer to Section [5.9](#).

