5.2.1.3 Study Discontinuation

Study discontinuation occurs when an enrolled patient ceases to participate in the study, regardless of the reason (as detailed under "Follow-up" in Section [5.2](#)). Patients have the right to withdraw consent at any time; if this is the case, no further study procedures should be performed.

The date and reason for study discontinuation will be clearly documented on the patient's CRF.

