5.9 FOLLOW-UP AFTER END-OF-TREATMENT VISIT

The date and reason of the study discontinuation will be recorded on the patient's CRF (see Section [5.2.1.1](#)).

Only patients who discontinue treatment without PD will have radiological evaluations during follow-up period. The assessments will be performed every two months during the first six months and every three months thereafter until PD, start of a new antitumor therapy, death, or until the end of study date (clinical cutoff). After PD is documented or

a new antitumor therapy is started, each cohort (except SCLC) will be followed-up at least every six months and up to 12 months after the last patient enrolled received the first PM01183 infusion (a documented phone contact will be acceptable). Patients in the SCLC cohort, after PD, will be followed-up every six months for at least 18 months after the last patient enrolled received the first PM01183 infusion (a documented phone contact will be acceptable).

The end-of-study date (clinical cutoff for each cohort except SCLC) is defined as the time point when all evaluable patients within each cohort have at least 12 months of follow-up from the first PM01183 infusion. Patients with SCLC will be followed-up for at least 18 months after the last patient enrolled received the first PM01183 infusion.

Patients who have withdrawn from the study treatment with an ongoing drug-related AE should be followed every four weeks until event recovery to at least grade 1 or stabilization or until onset of a new antitumor therapy.

Additional parameters and/or increased frequency of observations should be performed at the Investigator's discretion and according to the nature of the observed AEs. In case of death, autopsy data should be provided when available.

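### The stopping lists end treatment without exception when a third dose reduction is needed, while Section 6.6 allows dosing to continue; Sections 6.5 and 6.6 also call patients withdrawn from the trial whom they allow to be dosed

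*Protocol*

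**What the plan says.** Section 5.2.1.2 of the protocol lists the reasons for ending treatment. One item is "Requirement of > two dose reductions", with nothing attached to it. The item for a delay of more than three weeks does carry an exception, for clear clinical benefit with the Sponsor's approval. The same list, with the same asymmetry, appears in the synopsis (duration of study period per patient), in Section 3 and in SAP Section 2. After the list, 5.2.1.2 adds: "Patients who are withdrawn for any reasons must not be re-treated in the context of this study at any time". It then sends the reader to Section 5.9 for follow-up.

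Section 6.6 states: "Up to two dose reductions are allowed per patient". Patients with continuing treatment-related toxicity or frequent delays after that "must be withdrawn from the study. They can continue receiving the study medication if objective clinical benefit is adequately documented by the Investigator", subject to agreement with the Sponsor. The dose reduction part of the synopsis repeats this.

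Section 6.5, also repeated in the synopsis, is built the same way for delays: "Patients not meeting re-treatment criteria after a maximum 3-week delay must be withdrawn from trial". It continues: "In case of objective clinical benefit, the patient could continue receiving the treatment", again with the Sponsor's agreement.

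Sections 5.2.1.1 and 5.2.1.3 define two different events. Treatment discontinuation is ceasing to receive study treatment. For the other, "Study discontinuation occurs when an enrolled patient ceases to participate in the study".

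**The concern.** There are two faults, of different weight.

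The first is a contradiction in an operative stopping rule. A patient at the lowest dose level who needs a further reduction and has documented benefit is stopped under one set of passages and may be dosed under another. Exposure, the reason recorded for ending treatment and any protocol-deviation finding for that patient would depend on the section consulted.

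The second is terminology. A patient who may still receive study drug is described as withdrawn from the trial or the study, although the protocol separates stopping treatment from leaving the study and bars re-treatment of withdrawn patients. A site could record a toxicity stop as study discontinuation when the protocol elsewhere intends follow-up to continue.

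**Working it through.** No sample size, power or error rate enters here, so there is nothing to recompute. The check sets the passages side by side.

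**Who is affected by the first fault.** Table 7 gives a starting level of 3.2 mg/m², then 2.6 and 2.0. There is no lower level, and two reductions are the maximum. Having had two reductions does not end treatment under 5.2.1.2; such a patient may be treated at 2.0 mg/m². The item applies when a third reduction is required. Section 6.5 shows how that arises: a delay of more than one week due to treatment-related adverse events makes a reduction mandatory. At 2.0 mg/m² no tabulated reduction remains.

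**What each passage does with a patient who would need a third reduction.**

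| Situation | 5.2.1.2, Section 3, synopsis list, SAP Section 2 | 6.6 and its synopsis repeat |
|---|---|---|
| No documented benefit, or no Sponsor agreement | Treatment ends | Withdrawn |
| Documented benefit and Sponsor agreement | Treatment ends | May continue |

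The passages differ only in the second row. The synopsis contains both texts, so it contradicts itself.

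**Delay of more than three weeks.** Section 5.2.1.2 ends treatment unless there is clear clinical benefit and Sponsor approval. Section 6.5 withdraws the patient but allows treatment with objective clinical benefit and Sponsor agreement. On dosing the two agree.

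**The withdrawal wording.** Under Section 5.2 a patient is on-treatment for the duration of treatment until end of treatment, and on-study from consent until the end of follow-up. A patient being dosed is therefore on-study by definition and cannot also be withdrawn from the study. The protocol has a suitable term elsewhere: 6.6 itself speaks of discontinuing study treatment for severe hypersensitivity, and 5.9 refers to withdrawal from study treatment. The different wording in 6.5 and in the last paragraph of 6.6 invites a site to think something different is meant.

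**Follow-up.** Section 5.2.1.2 directs withdrawn patients to 5.9. There, "Only patients who discontinue treatment without PD will have radiological evaluations during follow-up period"; patients with an ongoing drug-related event are seen every four weeks, and contact for survival continues. The only event said to end all study procedures is withdrawal of consent (Sections 5.2 and 5.2.1.3).

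**The case against.** The strongest reply is that 6.5 and 6.6 each state a rule and then its exception. On that reading, a patient kept on drug under the exception was never withdrawn, so the re-treatment bar does not touch that patient. Re-treatment may also mean restarting rather than continuing; the text does not say. Both exceptions need the Sponsor's agreement, which gives a central check on sites.

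This answers much of the wording complaint, but not the first fault. Even as rule and exception, the exception in 6.6 is missing from all four stopping lists, and the delay item shows that the authors wrote an exception into the list for another criterion. The Sponsor's agreement decides who may use the exception; it does not say whether the exception exists.

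A reader might go further and infer that patients stopped for toxicity drop out of follow-up, so that safety data are lost and PFS, DR and OS are informatively censored. The documents do not support this. Section 5.2.1.2 points to 5.9 and Section 5.2 keeps a dosed patient on-study. Sections 7.7.1 and 7.7.2 collect adverse events until 30 days after the last dose or the start of a new antitumor therapy, and related serious events beyond that. The paper form for serious events after off-study carries the same 24-hour duty. In the SAP, Table 10.2.1 has a treatment-related adverse event category for ending treatment, while Table 10.2.5 has no toxicity category for leaving the study, so the analysis plan already treats a toxicity stop as a treatment event. What remains is a risk of misrecording at a site, not a planned loss of data.

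**Conclusion.** The point holds in a limited form. The documents contradict each other on one group: patients who would need a third reduction, have documented objective benefit and would obtain the Sponsor's agreement. The size of that group is not given. All these conditions must hold together, so it is probably small; that is a judgement, not a calculation. The toxicity rates in Section 1.12 do not help to size it, because they describe any occurrence at a given dose and not toxicity persisting after two reductions.

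For delays over three weeks there is no dosing conflict, only the withdrawal wording. That wording is wrong against the protocol's own definitions and could lead to misrecorded study discontinuations, but the follow-up provisions are in place. The primary analysis, sample size, alpha and power do not depend on this point. It should be corrected because it concerns when treatment stops and the correction is easy.

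**What to change.** Reconcile Section 5.2.1.2, Section 3, Section 6.6, both places in the synopsis (the dose reduction text and the stopping list) and SAP Section 2, so that the item on more than two reductions and the last paragraph of 6.6 state the same rule, with or without the benefit exception. Which of the two applies is for the sponsor's clinicians.

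In 6.5, 6.6 and their synopsis repeats, replace withdrawal from the trial or study by discontinuation of study treatment, and write each rule and any exception to it as one sentence. Section 5.9 follow-up then plainly applies to those who stop. Reword the re-treatment bar in 5.2.1.2 so that it refers to patients who have discontinued study treatment.

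The cost is one wording amendment to the protocol and a matching line in the SAP. No procedure, visit or analysis is added.
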